**Dose modification and toxicity management of infusion-reactions related to pembrolizumab**

Pembrolizumab may cause severe or life threatening infusion-reactions including severe hypersensitivity or anaphylaxis. Signs and symptoms usually develop during or shortly after drug infusion and generally resolve completely within 24 hours of completion of infusion. Dose modification and toxicity management guidelines on pembrolizumab associated infusion reaction are provided in Table 3.

**Table 3 Pembrolizumab Infusion Reaction Dose modification and Treatment Guidelines**

NCI CTCAE Grade	Treatment	Premedication at Subsequent Dosing

Grade 1 Mild reaction; infusion interruption not indicated; intervention not indicated
	
Increase monitoring of vital signs as medically indicated until the participant is deemed medically stable in the opinion of the investigator.
	
None

Grade 2 Requires therapy or infusion interruption but responds promptly to symptomatic treatment (e.g., antihistamines, NSAIDs, narcotics, IV fluids); prophylactic medications indicated for ≤24 hrs
	
Stop Infusion. Additional appropriate medical therapy may include but is not limited to: IV fluids Antihistamines NSAIDs Acetaminophen Narcotics Increase monitoring of vital signs as medically indicated until the participant is deemed medically stable in the opinion of the investigator. If symptoms resolve within 1 hour of stopping drug infusion, the infusion may be restarted at 50% of the original infusion rate (e.g. from 100 mL/hr to 50 mL/hr). Otherwise dosing will be held until symptoms resolve and the participant should be premedicated for the next scheduled dose. Participants who develop Grade 2 toxicity despite adequate premedication should be permanently discontinued from further study drug treatment
	
Participant may be premedicated 1.5h (± 30 minutes) prior to infusion of Pembrolizumab with: Diphenhydramine 50 mg po (or equivalent dose of antihistamine). Acetaminophen 500-1000 mg po (or equivalent dose of analgesic).


Grades 3 or 4 Grade 3: Prolonged (i.e., not rapidly responsive to symptomatic medication and/or brief interruption of infusion); recurrence of symptoms following initial improvement; hospitalization indicated for other clinical sequelae (e.g., renal impairment, pulmonary infiltrates) Grade 4: Life-threatening; pressor or ventilatory support indicated
	
Stop Infusion. Additional appropriate medical therapy may include but is not limited to: Epinephrine** IV fluids Antihistamines NSAIDs Acetaminophen Narcotics Oxygen Pressors Corticosteroids Increase monitoring of vital signs as medically indicated until the participant is deemed medically stable in the opinion of the investigator. Hospitalization may be indicated. **In cases of anaphylaxis, epinephrine should be used immediately. Participant is permanently discontinued from further study drug treatment.
	
No subsequent dosing

Appropriate resuscitation equipment should be available at the bedside and a physician readily available during the period of drug administration. For further information, please refer to the Common Terminology Criteria for Adverse Events v4.0 (CTCAE) at http://ctep.cancer.gov
		

**Other allowed dose interruption for pembrolizumab**

Pembrolizumab may be interrupted for situations other than treatment-related AEs such as medical / surgical events or logistical reasons not related to study therapy. Participants should be placed back on study therapy within 3 weeks of the scheduled interruption, unless otherwise discussed with the Sponsor. The reason for interruption should be documented in the patient's study record.

**5.2.3 Second Course\***

All participants who top study treatment with stable disease (SD) or better may be eligible for up to an additional 17 cycles (approximately 1 year) of pembrolizumab treatment if they progress after stopping study treatment from the initial treatment phase. This retreatment is termed the Second Course Phase of this study and is only available if the study remains open and the participant meets the following conditions:

**Either**

- Stopped initial treatment with study treatment after attaining an investigator-determined confirmed CR based on RECIST 1.1, and
  - Was treated with at least 8 cycles of study treatment before discontinuing treatment, and

- Received at least 2 treatments with pembrolizumab beyond the date when the initial CR was declared

**OR**

- Had SD, PR, or CR and stopped study treatment after completion of 35 administrations (approximately 2 years) of study treatment for reasons other than disease progression or intolerability

**AND**

- Experienced an investigator-determined radiographic disease progression by RECIST 1.1 after stopping initial treatment, and
  - Upon unblinding at the time of centrally verified disease progression were found to have received pembrolizumab, and
  - No new anticancer treatment was administered after the last dose of study treatment, and
  - The participant meets all of the safety parameters listed in the inclusion criteria and none of the safety parameters listed in the exclusion criteria, and
  - The study is ongoing

An objective response or disease progression that occurs during the Second Course Phase for a participant will not be counted as an event for the primary analysis of either endpoint in this study.

*\*Note: patients must have measurable disease at the start of protocol treatment to be eligible for this provision.*

**5.3 Concomitant Medications/Vaccinations (allowed & prohibited)**

Medications or vaccinations specifically prohibited in the exclusion criteria are not allowed during the ongoing trial. If there is a clinical indication for one of these or other medications or vaccinations specifically prohibited during the trial, discontinuation from trial therapy or vaccination may be required. The final decision on any supportive therapy or vaccination rests with the investigator and/or the participants's primary physician.

**5.3.1 Acceptable Concomitant Medications**

All treatments that the investigator considers necessary for a participant's welfare may be administered at the discretion of the investigator in keeping with the community standards of medical care. All concomitant medication will be recorded on the case report form (CRF) including all prescription, over-the-counter (OTC), herbal supplements, and IV medications and fluids. If changes occur during the trial period, documentation of drug dosage, frequency, route, and date may also be included on the CRF.

All concomitant medications received within 28 days before the first dose of trial treatment and 30 days after the last dose of trial treatment should be recorded. Concomitant medications administered after 30 days after the last dose of trial treatment should be recorded for SAEs and ECIs as defined in Section 7.2.

### 5.3.2 Prohibited Concomitant Medications

Participants are prohibited from receiving the following therapies during the Screening and Treatment Phase (including retreatment for post-complete response relapse) of this trial:

- Antineoplastic systemic chemotherapy or biological therapy
- Immunotherapy not specified in this protocol
- Chemotherapy not specified in this protocol
- Investigational agents other than pembrolizumab
- Radiation therapy
  - Note: Radiation therapy to a symptomatic solitary lesion or to the brain may be allowed at the investigator's discretion.
- Live vaccines within 30 days prior to the first dose of study treatment and while participating in the study. Examples of live vaccines include, but are not limited to, the following: measles, mumps, rubella, varicella/zoster, yellow fever, rabies, BCG, and typhoid vaccine. Seasonal influenza vaccines for injection are generally killed virus vaccines and are allowed; however, intranasal influenza vaccines (eg, FluMist®) are live attenuated vaccines and are not allowed.
- Systemic glucocorticoids for any purpose other than to modulate symptoms from an event of clinical interest of suspected immunologic etiology. The use of physiologic doses of corticosteroids may be approved after consultation with the Sponsor.

Participants who, in the assessment by the investigator, require the use of any of the aforementioned treatments for clinical management should be removed from the study. All treatments that the Investigator considers necessary for a participant's welfare may be administered at the discretion of the Investigator in keeping with the community standards of medical care.

Medications or vaccinations specifically prohibited in the exclusion criteria are not allowed during the ongoing study. If there is a clinical indication for any medication or vaccination specifically prohibited during the study, discontinuation from study therapy or vaccination may be required. The final decision on any supportive therapy or vaccination rests with the investigator and/or the participant's primary physician. However, the decision to continue the participant on study treatment requires the mutual agreement of the investigator, the Sponsor and the participant.

There are no prohibited therapies during the Post-Treatment Follow-up Phase.

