### 5.1.2 Exclusion Criteria

Participant is excluded from the study if any of the following criteria apply:

1. Has HER2-positive breast cancer (FISH/CISH confirmed status, or 3+ IHC status)
2. Has use of any investigational agent or participation in another therapeutic clinical trial concurrently or in the 30 days prior to inclusion.
3. Has not recovered (e.g. to  $\leq$ Grade 1 or to baseline) from AEs due to a previously administered therapy. Note: Participants with  $\leq$ Grade 2 neuropathy may be eligible.
4. Has an active autoimmune disease that has required systemic treatment in the past 2 years (e.g. with the use of disease modifying agents, corticosteroids or immunosuppressive drugs). Replacement therapy (e.g., thyroxine, insulin or physiologic corticosteroid replacement therapy for adrenal or pituitary insufficiency) is not considered a form of systematic treatment.
5. Has a diagnosis of immunodeficiency or is receiving systematic steroid therapy or any other form of immunosuppressive therapy within 7 days prior to study treatment.
6. Has a concurrently active second malignancy, other than adequately treated non-melanoma skin cancers, in situ melanoma or in situ cervical cancer. Subjects with other non-mammary malignancies must have been disease-free for at least 5 years.
7. Has known active CNS metastases and/or carcinomatous meningitis. Previously treated brain metastases may participate provided these remain stable.
8. Has received prior therapy with an anti-PD1, anti-PDL1 or anti-PDL2 agent or with an agent directed to another co-inhibitory T cell receptor (such as CTLA-4, OX-40, and CD137) or has previously participated in pembrolizumab clinical studies.
9. Patient who has received a live vaccine within 30 days of the first dose of study drug.
10. Known hypersensitive or allergy to pembrolizumab and any of its components.
11. Patient who is pregnant or breastfeeding.
12. Patient with an expected life expectancy of less than 3 months.
13. History of significant comorbidities that, in the opinion of the investigator, may interfere with the conduct of the study, the evaluation of response, or with informed consent.
14. Active uncontrolled infection at the time of inclusion.
15. Has a history of class II-IV congestive heart failure or myocardial infraction.
16. Has known psychiatric or substance abuse disorders that would interfere with cooperation with the requirements of this study

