**Table 2 Dose modification and toxicity management guidelines for immune-related AEs associated with pembrolizumab**

General instructions:				

 
1. Corticosteroid taper should be initiated upon AE improving to Grade 1 or less and continue to taper over at least 4 weeks.
 
2. For situations where pembrolizumab has been withheld, pembrolizumab can be resumed after AE has been reduced to Grade 1 or 0 and corticosteroid has been tapered. Pembrolizumab should be permanently discontinued if AE does not resolve within 12 weeks of last dose or corticosteroids cannot be reduced to <math>\leq 10</math> mg prednisone or equivalent per day within 12 weeks.
 
3. For severe and life-threatening irAEs, IV corticosteroid should be initiated first followed by oral steroid. Other immunosuppressive treatment should be initiated if irAEs cannot be controlled by corticosteroids.
 
				
Immune-related AEs	Toxicity grade or conditions (CTCAEv4.0)	Action taken to pembrolizumab	irAE management with corticosteroid and/or other therapies	Monitor and follow-up
Pneumonitis	Grade 2	Withhold	
 
• Administer corticosteroids (initial dose of 1-2 mg/kg prednisone or equivalent) followed by taper
 
	
 
• Monitor participants for signs and symptoms of pneumonitis
 
• Evaluate participants with suspected pneumonitis with radiographic imaging and initiate corticosteroid treatment
 
• Add prophylactic antibiotics for opportunistic infections
 

	Grade 3 or 4, or recurrent Grade 2	Permanently discontinue		
Diarrhea / Colitis	Grade 2 or 3	Withhold	
 
• Administer corticosteroids (initial dose of 1-2 mg/kg prednisone or equivalent) followed by taper
 
	
 
• Monitor participants for signs and symptoms of enterocolitis (ie, diarrhea, abdominal pain, blood or mucus in stool with or without fever) and of bowel
 

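### Section 5.3.2 names the wrong class of event in its steroid exception, and removes participants from the study where the rest of the protocol keeps them in follow-up

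*Protocol*

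**What the plan says.** Section 5.3.2 lists therapies prohibited during the screening and treatment phase. The last item is "Systemic glucocorticoids for any purpose other than to modulate symptoms from an event of clinical interest of suspected immunologic etiology", with physiologic doses possible after consulting the Sponsor. Participants who, in the investigator's assessment, "require the use of any of the aforementioned treatments for clinical management should be removed from the study". The section then softens this. The investigator may give whatever the participant's welfare needs, a clinical need for a prohibited medication may require stopping study therapy, and "the decision to continue the participant on study treatment requires the mutual agreement of the investigator, the Sponsor and the participant". It closes by lifting all prohibitions in the post-treatment follow-up phase.

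Section 7.2.3.2 lists two events of clinical interest (ECIs). One is an overdose without symptoms or abnormal laboratory results. The other is AST or ALT at least 3 times the upper limit of normal, with bilirubin at least 2 times and alkaline phosphatase below 2 times that limit.

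Table 2 directs corticosteroids for immune-related AEs. After a withheld dose, "pembrolizumab can be resumed after AE has been reduced to Grade 1 or 0 and corticosteroid has been tapered". Section 5.4 has participants who stop for unacceptable adverse experiences under 5.2.2 leave treatment but stay under monitoring.

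**The concern.** The exception borrows a term that the protocol uses elsewhere for a short expedited-reporting list. Pneumonitis, colitis and nephritis, for which Table 2 directs steroids, are not on that list. A reader who looks the term up finds that steroid treatment of Grade 2 pneumonitis falls outside the exception. The next rule in 5.3.2 then takes the participant out of the study, while Table 2 says to withhold, treat, taper and resume.

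The removal rule is a problem in its own right, because it attaches to every listed therapy. In a single-arm trial with follow-up-dependent secondary endpoints, leaving the study is a different matter from leaving treatment. The first loses later scans and survival contacts; the second does not.

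**Working it through.** The plan states no figure on this point, so the check compares the sections. The only counting is of table rows.

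1. **Is the term tied to a list?** Yes. Section 5.3.1 sends the reader to section 7.2 for the definition of ECIs, and note c to the flow charts in 6.1 and 6.2 points to section 7.2.3.2. The lead-in there is worded inclusively, but only the two items follow.

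2. **How does the list match Table 2?** Table 2 has ten rows. Three (type 1 diabetes or hyperglycemia, hyperthyroidism, hypothyroidism) direct no steroid. The other 10 − 3 = 7 do: pneumonitis, diarrhea/colitis, liver tests, hypophysitis, nephritis, myocarditis, and all other immune-related AEs. Six of the seven are wholly outside the two listed ECIs. The liver row is partly outside: raised transaminases or raised bilirubin alone triggers it, whereas the ECI needs both plus the alkaline phosphatase condition. This shows the term does not fit; it does not measure harm.

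3. **Where does the steroid wording conflict with Table 2?** In the rows and grades where drug is withheld and may resume: Grade 2 pneumonitis, Grade 2 or 3 colitis, Grade 2 liver abnormality, Grade 2 hypophysitis, Grade 2 nephritis, Grade 1 or 2 myocarditis, and intolerable or persistent Grade 2 and some Grade 3 other events. Where Table 2 requires permanent discontinuation, the participant moves to post-treatment follow-up. Section 5.3.2 prohibits nothing there, so the steroid conflict largely falls away.

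4. **Does the removal rule agree with the rest of the protocol?** However the ECI term is read, it does not:

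| Situation | 5.3.2 removal sentence | Other rule |
|---|---|---|
| Needs any listed therapy | Out of the study | 5.3.2, two sentences later: stopping study therapy is only a possibility, and continuing by agreement is allowed |
| Starts new anticancer therapy | Out of the study | 7.1.1.5.3 and 7.1.5.3.3: survival follow-up, telephone contact every 12 weeks |
| Stops drug without progression | Out of the study | 7.1.2.6.3 and 7.1.5.3.2: imaging continues every 9 weeks in year 1, then every 12 weeks |
| Stops for an unacceptable AE under 5.2.2 | Out of the study if a listed therapy is needed | 5.4: stops drug, stays monitored |

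Section 5.4 does not itself name use of a prohibited medication as a reason. The conflict with 5.4 is therefore indirect, through the adverse-experience reason. The conflict with 7.1.1.5.3 is direct.

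5. **What does removal do to the analysis?** Section 8.5 places a participant in the Full Analysis Set (FAS) on one dose and a measurable baseline scan, so someone removed later stays in the set. PFS and DOR need progression or death to be observed, DCR is assessed at 6, 12 and 24 months, and OS needs survival status. Removal ends the scans or the contacts that supply these. The exit is prompted by toxicity or by the need for other treatment, so it is unlikely to be independent of outcome, and Kaplan–Meier estimates censored there would carry that dependence. The documents do not show the direction or the size.

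**The case against.** The strongest reply is that nobody would read the exception literally. The qualifier about immunologic etiology, section 5.2.2 and section 5.3.3 all point to immune-related AEs. The literal reading would also leave the exception almost empty, since an overdose without symptoms gives a steroid nothing to treat. This stands. It settles what the authors meant and limits the practical harm, but it does not correct the term or the removal sentence. The softer wording in 5.3.2 covers the steroid item as well as the rest. It weakens the removal rule but also leaves the section inconsistent with itself.

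Three stronger readings might be inferred, and the documents do not support them.

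- *The protocol bans steroids for immune-related AEs.* It does not. Table 2 and 5.3.3 direct them, and 5.3.2 leaves necessary care to the investigator.
- *A second, independent ban arises from the exclusion criteria.* Sections 5.3 ("Medications or vaccinations specifically prohibited in the exclusion criteria are not allowed during the ongoing trial") and 5.3.2 ("Medications or vaccinations specifically prohibited in the exclusion criteria are not allowed during the ongoing study") carry those prohibitions forward, and exclusion 5 covers a participant "receiving systematic steroid therapy or any other form of immunosuppressive therapy within 7 days prior to study treatment". Table 2 meanwhile says "Other immunosuppressive treatment should be initiated if irAEs cannot be controlled by corticosteroids". But exclusion 5 is an entry criterion with a pre-treatment window. On-study steroids have their own item with an exception, and the specific item governs the general sentence. The stated consequence is also only a possible discontinuation. This is not a separate defect.
- *The loss can be expressed in scans or in points of response rate.* Any scan count assumes a date of removal and no progression afterwards. The phase Ib study in triple-negative disease summarised in 4.2.1.1 had a 6-month PFS rate of 24%, so imaging would often have ended anyway. One participant's share of the response rate is only the reciprocal of the sample size.

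**Conclusion.** Section 5.3.2 is wrong as written on two counts: the term in the steroid exception, and the instruction to remove participants from the study. The first conflicts with Table 2 only when taken literally and only where drug is withheld and may resume. The second conflicts with its own section and with the follow-up rules under any reading of the ECI term.

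The severity is minor. The harm requires a site to apply the removal sentence in preference to Table 2 and the follow-up sections, and most sites would not. The protocol gives no rate of immune-related AEs, steroid use or prohibited-therapy use, so the number affected cannot be estimated. For any participant removed, the loss is concrete: she remains in the FAS with later disease or survival information missing after an exit related to her condition.

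**What to change.** Make two replacements in section 5.3.2:

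1. In the glucocorticoid item, replace the reference to an event of clinical interest of suspected immunologic etiology with *an immune-related AE or infusion reaction managed per Tables 2 and 3*. Table 3 is named because it lists corticosteroids for Grade 3 or 4 infusion reactions.
2. In the removal sentence, replace removal from the study with *discontinued from study treatment (unless continuation is agreed as below) and followed per Sections 5.4 and 7.1.5.3*.

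The second change applies to every listed therapy. That is appropriate, because the follow-up rules already cover participants who stop drug or start new treatment. The ECI list in 7.2.3.2, exclusion 5 and the general sentences in 5.3 can stay as they are. The cost is wording only, with no new procedure and no change to directed care, eligibility or safety reporting.

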### 5.3.3 Rescue Medications & Supportive Care

Participants should receive appropriate supportive care measures as deemed necessary by the treating investigator. Suggested supportive care measures for the management of AEs with potential immunologic etiology are outlined along with the dose modification guidelines in Section 5.2.2, [Table 2]. Where appropriate, these guidelines include the use of oral or IV treatment with corticosteroids, as well as additional anti-inflammatory agents if symptoms do not improve with administration of corticosteroids. Note that several courses of steroid tapering may be necessary as symptoms may worsen when the steroid dose is decreased. For each disorder, attempts should be made to rule out other causes such as metastatic disease or bacterial or viral infection, which might require additional

supportive care. The treatment guidelines are intended to be applied when the Investigator determines the events to be related to pembrolizumab.

Note: If after the evaluation of the event, it is determined not to be related to pembrolizumab, the Investigator does not need to follow the treatment guidance. Refer to Table 2 in for guidelines regarding dose modification and supportive care.

It may be necessary to perform conditional procedures such as bronchoscopy, endoscopy, or skin photography as part of evaluation of the event.

